- d Nasal exam will only be performed at Visit 6 if any abnormality on exam at Visit 5 or any report of a nasal cavity AE
- e Chemistry panel only: triggered serum osmolality will be measured from same specimen if sodium is below the lower limit of normal
- f Urinalyses, hematology and chemistry labs will only be repeated at Visit 6 if clinically significant findings were observed at Visit 5
- Women of childbearing potential only: screening serum pregnancy test will be analyzed at Central laboratory; consecutive urine pregnancy tests will be conducted on-site at every subsequent study visit
- h Urine drug test: cocaine, phencyclidine (PCP), barbiturates, amphetamines, cannabis, and opiates
- i C-SSRS: Columbia Suicide Severity Rating Scale
- MSI-BPD: McLean Screening Instrument for Borderline Personality Disorder
- k E-diary training will be conducted at Visit 1 (Screening Visit) and Visit 2 (Treatment) and will be repeated at Visits 3 and 4. E-diary is collected at Visit 5
- Patients will start completing their e-diary the day after their Screening Visit.
- Study drug administration training performed at Visit 2 in addition to dispensation of study drug
- n PGIC: Patient Global Impression of Change
- ° HADS: Hospital Anxiety and Depression Scale
- p MIDAS: Migraine Disability Assessment questionnaire
- q MSQ: Migraine-Specific Quality of Life Questionnaire v2.1
- r CSFQ-14: Changes in Sexual Functioning Questionnaire Short-Form
- Pharmacogenomics should be drawn at Baseline but if it is not drawn, drawing at a subsequent visit is allowed.
- Placebo Response training will be conducted in the form of a video that patients watch at Visit 1. At subsequent visits (V2-V5), training will be conducted via a paper script that the site staff reviews with the patient.

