# 5.7 Treatment Compliance

Treatment compliance will be monitored via the e-diary. The e-diary will be used to log headaches and abortive medications, but once patients are randomized into the study and starts the study drug, they will also be required to report whether they have taken their morning dose and evening dose on a daily basis. Please refer to Section 6.8.5 for additional details on the e-diary.

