# 6.8.5 E-Diary Assessments

The daily diary is an important aspect of this study, and all patients must receive training explaining what is being asked of them, when to complete the diary, and how to use the diary system effectively.

On Visit 1, patients will be shown how to download the app to their iPhone or Android smartphone, will be provided with the credentials for opening the e-diary app, and assisted in entering the patient's specific typically used abortive medications for migraines. In addition, the site should set up the e-diary notifications for the patient within the IRT and the ePRO application.

On V2, V3, and V4, diary compliance should be reviewed, and patients should receive retraining as needed.

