### 7.3. Measures of Treatment Compliance

No direct measures of drug compliance will be captured via drug accountability. Compliance via the diary will be reported for the post-baseline period. Patients are asked to report whether they took their morning and evening doses; compliance will be reported as the number of “Yes” responses reported out of the total number of expected doses based on the dates the diary was issued and collected times 2 doses/day. The compliance will be summarized with descriptive statistics. Additionally, the number and percentage of patients with <70% compliance, 70% to <80%, 80% to <90%, and 90 to 100% compliance will be reported.

Additionally, compliance with diary completion will be reported and summarized with descriptive statistics. Diary compliance will be defined as the number of days which have ANY data entered (even if partial/incomplete) divided by the number of days they were expected to complete the diary. This will be summarized for the baseline and post-baseline periods separately.

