a An Early Termination Visit will be conducted approximately 7 days (+3 days) of withdrawing from study

b Follow-up visit will be conducted approximately 14 days (+ 4 days) after Visit 5

c Record any changes to the medication history obtained at Screening

d Nasal exam will only be performed at Visit 6 if any abnormality on exam at Visit 5 or any report of a nasal cavity AE

e Chemistry panel only: triggered serum osmolality will be measured from same specimen if sodium is below the lower limit of normal

f Urinalyses, hematology and chemistry labs will only be repeated at Visit 6 if clinically significant findings were observed at Visit 5

g Women of childbearing potential only: screening serum pregnancy test will be analyzed at Central laboratory; consecutive urine pregnancy tests will be conducted on-site at every subsequent study visit

h Urine drug test: cocaine, phencyclidine (PCP), barbiturates, amphetamines, cannabis, and opiates

Page 42 of 51

Version Date: 2023-11-16

Version: 1.0

Tonix Pharmaceuticals  
Statistical Analysis Plan: TNX-OX-CM201

- i C-SSRS: Columbia Suicide Severity Rating Scale
- j MSI-BPD: McLean Screening Instrument for Borderline Personality Disorder
- k E-diary training will be conducted at Visit 1 (Screening Visit) and Visit 2 (Treatment) and will be repeated at Visits 3 and 4. E-diary is collected at Visit 5.
- l Patients will start completing their e-diary the day after their Screening Visit.
- m Study drug administration training performed at Visit 2 in addition to dispensation of study drug
- n PGIC: Patient Global Impression of Change
- o HADS: Hospital Anxiety and Depression Scale
- p MIDAS: Migraine Disability Assessment questionnaire
- q MSQ: Migraine-Specific Quality of Life Questionnaire v2.1
- r CSFQ-14: Changes in Sexual Functioning Questionnaire Short-Form
- s Pharmacogenomics should be drawn at Baseline but if it is not drawn, drawing at a subsequent visit is allowed.

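### SAP 7.3 counts expected doses from diary issue to diary collection, dates that conflict with its own post-baseline restriction and can turn undosed days into missed doses

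*SAP*

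**What the plan says.** Protocol 5.7 makes the diary the instrument for adherence: "Treatment compliance will be monitored via the e-diary". SAP 7.3 adds that drug accountability will give no direct measure of drug compliance.

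SAP 7.3 then sets the scope: "Compliance via the diary will be reported for the post-baseline period". The next sentence defines the ratio. The numerator is the count of Yes answers to the morning and evening dose questions. The denominator is the "total number of expected doses based on the dates the diary was issued and collected times 2 doses/day". Results are summarised descriptively and by band: "<70% compliance, 70% to <80%, 80% to <90%, and 90 to 100% compliance will be reported".

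The diary dates come from elsewhere:

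- **Set-up.** Protocol 6.8.5: "On Visit 1, patients will be shown how to download the app to their iPhone or Android smartphone".
- **First entry.** Protocol Schedule of Assessments, footnotes: "Patients will start completing their e-diary the day after their Screening Visit".
- **Collection.** SAP 15.1, footnotes: "E-diary is collected at Visit 5".
- **Visit 2.** Protocol 8.2 lists diary review and re-training, with no new issue of the diary.
- **Dose questions.** Protocol 5.7 and 6.8.5.2 and SAP 15.4 have doses logged only once treatment has started.

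**The concern.** Two adjacent sentences in SAP 7.3 point to different start dates. The scope sentence implies randomization. The formula names diary issue, and the only issue event in the documents is at Screening, at least 28 days before the first dose. A program written from the formula alone would add run-in days, on which no dose is due, to the denominator.

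The end date is loose in a different way. Collection happens at Visit 5 or the Early Termination Visit, which may fall after the patient has stopped study drug. Correcting the start date does not cure this.

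At stake is how adherence is read in a proof-of-concept trial. If the result is null, readers will ask whether patients took the drug. The same dosing behaviour could be reported as about 100% or as 60-75%, depending on how one sentence is coded.

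**Working it through.** The plan states no expected compliance value, so there is no figure of its own to reproduce. The check asks what a fully adherent patient would score under each reading.

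**Inputs**

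- Treatment days T: about 84 (Protocol 3.1, SAP 3).
- Doses per day: 2 (SAP 7.2), so 84 × 2 = 168 doses.
- Pre-randomization diary days R: at least 28, plus up to 21 for washout, giving 49 (Protocol 3.1, SAP 3).
- Run-in extension: up to 7 days (Protocol Schedule of Assessments, starred footnote). R = 49 + 7 = 56 assumes that the full washout and the full extension can be added together.
- Early Termination Visit: about 7 days, +3, after withdrawal (Schedule of Assessments, footnote a).

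**Start date, literal reading.** Score = 2T / [2(T + R)] = T / (T + R).

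| R (days) | Calculation | Score |
|---|---|---|
| 28 | 84/112 | 75.0% |
| 35 | 84/119 | 70.6% |
| 49 | 84/133 | 63.2% |
| 56 | 84/140 | 60.0% |

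To reach 80% on this reading, R could be at most 84/0.8 − 84 = 21 days, below the 28-day minimum. Alternatively, with R = 28, T would have to be 0.8 × 28/0.2 = 112 days. A late Visit 5 does not help: T = 88 or 89 with R = 28 gives 75.9% or 76.1%. The upper two bands would be empty.

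**Start date, post-baseline reading.** R = 0, so the score is 168/168 = 100%. If the Visit 5 day (Day 85) is counted as two expected doses, the denominator is 85 × 2 = 170. The score is then 168/170 = 98.8% if no Visit 5 dose is logged, or 169/170 = 99.4% if the morning dose is. Protocol 5.2 has only the morning dose taken before the bottles are collected that day, so counting two overstates what was due.

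**End date, early terminators, starting at first dose.** The assumption is that the last dose is taken at withdrawal and the diary is collected g days later, with g = 7 to 10. Score = d / (d + g) for d fully adherent days.

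| d (days) | g = 7 | g = 10 |
|---|---|---|
| 14 | 14/21 = 66.7% | 14/24 = 58.3% |
| 28 | 28/35 = 80.0% | 28/38 = 73.7% |
| 56 | 56/63 = 88.9% | 56/66 = 84.8% |

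A visit sooner after withdrawal, which Protocol 4.4 encourages, would shrink this effect.

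**The case against.** The best defence is that SAP 7.3 must be read whole. The scope sentence comes immediately before the formula and governs it. The formula counts expected doses, and none are expected before randomization. The documents nowhere define diary issue as Visit 1; that is an inference from the only set-up described. A careful programmer would probably start at first dose and get about 100%.

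Much of this stands. A reader might infer from the formula that no patient could reach the 80% band and that the SAP's definition is simply wrong. The documents do not support that: it is true only if the formula is coded without the sentence before it. What remains is that the intended start date is never named, and the one date that is named fits the stated scope badly.

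A reader might also infer that this is the trial's only evidence on adherence. SAP 10.2 separately plans duration of exposure from CRF first and last dose dates, and exposure days based on the diary. Neither depends on run-in length, and both would make an implausible compliance table easy to spot.

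Nor do the documents support an inference of bias between arms from the start date, because the run-in precedes randomization. The end-date effect could differ between arms if discontinuation does, but its size rests on assumed visit timing.

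**Conclusion.** SAP 7.3 is internally inconsistent on the start of the compliance denominator and imprecise on its end. For a fully adherent 84-day patient, the literal reading gives 75% down to 63% for run-ins of 28 to 49 days, or 60% with the extension added. The post-baseline reading, which the paragraph as a whole favours, gives about 99-100%. Under either start date, diary collection can count days after withdrawal as missed doses: 74-80% for 28 adherent days, given collection 7 to 10 days after a last dose at withdrawal.

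The consequence is confined to one descriptive table and how it is read. Compliance defines none of the populations in SAP 4 and does not enter the primary model in SAP 9.1.2. This is a definition to correct before programming; it does not threaten the efficacy conclusions.

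**What to change.** In SAP 7.3, replace the reference to diary issue and collection dates with a denominator that:

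- starts at the first-dose date, as already used in SAP 10.2;
- ends at Visit 5 for patients who remain in the study, or at the date of withdrawal for early terminators;
- counts the first and last days by the doses actually due, so that a Visit 5 on Day 85 contributes one dose and the total is 84 × 2 + 1 = 169.

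Do not end the denominator at the last-dose date for patients still in the study. Someone who stopped dosing early but stayed to Visit 5 would then score 100%, which would hide the non-adherence the table is meant to show.

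The cost is a sentence or two in the SAP and the matching programming specification. No new data should be needed, assuming a withdrawal date is recorded at discontinuation; the documents do not name the field.

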## **8. GENERAL ANALYSIS AND REPORTING CONSIDERATIONS**

Descriptive summaries will be provided where appropriate for each of the primary and secondary variables. In general, tables will summarize data by treatment group and visit.

Continuous, quantitative variable summaries will include the number of patients (N) with non-missing values, mean, standard deviation, median, minimum, and maximum.

Categorical, qualitative variable summaries will include the frequency and percentage of patients who are in the particular category. In general, the denominator for the percentage calculation will be based upon the total number of patients in the study population for the treatment group unless otherwise specified.

Unless otherwise specified, baseline values are defined as the last non-missing measurement prior to the first dose of study drug. Change from baseline will be defined as the post-baseline visit value minus the baseline value.

For continuous endpoints where treatment groups are compared via linear models with the difference in LS means, the effect size will be calculated and included as a summary statistic using the difference in LS means and its standard error, transformed to a standard deviation. Study day is defined as assessment date – first dose date +1 for dates after the first dose date and assessment date – first dose date for dates prior to the first dose.

All analyses will be performed using SAS® Software version 9.4 or later.

### **8.1.1. Study Success**

[REDACTED]

### **8.1.2. Multicenter Studies**

This is a multicenter study. Unless otherwise specified, data from all study sites will be pooled for all analyses unless otherwise specified.

### **8.1.3. Assessment Time Windows**

Patients who withdraw/drop out from the study will have the early termination (ET) data collected at their ET visit included in the analysis at the closest visit where a given assessment should be collected per the schedule of assessments (Week 4, 8, 12, 14), using midpoints

between visits to window the early termination. If this results in two records for a given visit, then the one closest to the targeted date will be used. Visits beyond day 112 (two weeks past the target day for Week 14) will not be mapped and reported with Week 14; they may appear in the last observation analyses described for safety endpoints.

Diary data will be grouped into 28 day “months” see section [9.1.1](#) for details.

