# 6.8.3 Migraine Disability Assessment Questionnaire

The Migraine Disability Assessment Test (MIDAS) is a patient-reported test used to determine how severely migraines affect a patient's life. At Visits 2 and 5, patients are asked questions about the frequency and duration of their headaches, as well as how often these headaches limited their ability to participate in activities at work, at school, or at home.

The questionnaire contains 5 scored questions and 2 supplemental questions:

- 1. On how many days in the last 3 months did you miss work or school because of your headaches?
- 2. How many days in the last 3 months was your productivity at work or school reduced by half or more because of your headaches? (do not include days you counted in question 1 where you missed work or school.)
- 3. On how many days in the last 3 months did you not do household work because of your headaches?
- 4. How many days in the last 3 months was your productivity in household work reduced by half or more because of your headaches? (do not include days you counted in question 3 where you did not do household work.)
- 5. On how many days in the last 3 months did you miss family, social or leisure activities because of your headaches?
- A. On how many days in the last 3 months did you have any headache? (If a headache lasted more than one day, count each day)
- B. On a scale of 0 10, on average how painful were these headaches? (where 0 = no pain at all, and 10 = pain which is as bad as it can be)

Only questions 1-5 contribute to the score of the assessment. The score obtained gives a measure of the extent of debilitation a patient's migraines:

0 to 5, MIDAS Grade I, Little or no disability
6 to 10, MIDAS Grade II, Mild disability
11 to 20, MIDAS Grade III, Moderate disability
21+, MIDAS Grade IV, Severe disability

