# 8.4 Visit 5 (Week 12) or Early Termination Visit

Visit 5 should occur after 12 weeks of double-blind study drug treatment. At this visit, the patient will return all study drug. The following assessments are completed:

- Assess changes in medication history and concomitant medications
- Assess occurrence of AEs
- Conduct a physical examination, including vital signs, weight
- Conduct a nasal cavity examination
- Conduct a 12-lead ECG
- Obtain blood for clinical laboratory tests (hematology, standard blood chemistry panel, urinalysis)
- Perform in-clinic urine pregnancy test (for WoCBP)
- Obtain blood sample for optional pharmacogenomics (after the separate ICF has been signed for pharmacogenomic substudy) if not drawn at a prior visit
- Have the patient complete placebo response training
- Administer the "Since Last Visit" version of the C-SSRS. Results of the C-SSRS should be reviewed to ensure the patient is not experiencing suicidal ideation or has had suicidal behavior that requires emergency intervention
- Have the patient complete:
  - 1. PGIC: Patient Global Impression of Change
  - 2. HADS: Hospital Anxiety and Depression Scale
  - 3. MIDAS: Migraine Disability Assessment questionnaire
  - 4. MSQ: Migraine-Specific Quality of Life Questionnaire v2.1
  - 5. CSFQ-14: Changes in Sexual Functioning Questionnaire Short-Form
- Review completed diary data and diary compliance with the patient. Provide re-training as needed.
- Assess study drug compliance and collect previously dispensed study drug and bottles
- After all the assessments at each visit have been completed, the patient should be given an appointment to return to the clinic for the Follow-up visit.

All patients who withdraw early from the study will be encouraged to complete the ET Visit for safety evaluations (Visit 5) within 7 days from withdrawal of study, followed by a Safety Follow-up Visit (Visit 6) approximately 14 days from the last study drug administration.

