# **8.6** Early Termination (After Randomization)

In accordance with the Declaration of Helsinki, patients have the right to withdraw from the study at any time for any reason, and they will be advised of this right. The investigator and Tonix also have the right to remove patients from the study. Specific reasons for removal of a patient from the study could include, but are not limited to:

- An AE
- An illness that, in the judgment of the investigator or Tonix, might invalidate the study data or place the patient at risk
- The request of the patient, investigator, or Tonix, whether for administrative or other reasons
- Pregnancy

Patients who wish to terminate their participation in the study should be instructed to come to the clinic for an ET Visit. The purpose of the ET Visit is to obtain critical information about the patient's participation and should be scheduled preferably before there has been a substantial lapse in study drug usage. However, even if there has been a drug lapse, the

patient should be encouraged to return to the clinic for this visit and should be instructed to return all study drug and bottles. Additionally, the patient should be encouraged to also subsequently attend the Safety Follow-Up Visit (Visit 6). NOTE: These visit procedures are not intended for patients who fail to qualify for randomization or for patients who withdraw from the study prior to receipt of a dose of double-blind study drug.

In addition to documenting the reason for ET during the ET visit, assessments and procedures should be completed according to the V5 schedule. For the Safety Follow-Up Visit (Visit 6), assessments and procedures should be completed according to the V6 schedule.

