### **9.2.2. Additional Secondary Endpoints**

Each of the following continuous endpoints will be summarized:

- Mean change from Baseline in the Hospital Anxiety and Depression Scale (HADS) at Week 12.
- Mean change from Baseline in the Migraine Disability Assessment questionnaire (MIDAS) Test total score at Week 12.
- Mean change from Baseline in patient-rated Changes in Sexual Functioning Questionnaire Short-Form (CSFQ-14) total score in males and in females, analyzed separately, at Week 12.

For each, summary statistics (mean, SD, median, minimum, maximum) will be reported for the change from the baseline to each visit and for each of the treatment groups.

For HADS the change from baseline will be analyzed in an MMRM model with fixed effects of treatment, visit, baseline value, treatment by visit interaction, and stratification factor (preventive medication use); an unstructured covariance matrix will be used. LSMS, standard errors, and the LSM differences (each treatment vs placebo) with 95% CIs and p-values will be reported for each visit (with week 12 being of primary interest). Denominator degrees of freedom will use the Kenward Rogers approach. Should the model fail to converge, heterogeneous Toeplitz, heterogeneous first-order autoregressive, Toeplitz, first order autoregressive and compound symmetric will be attempted in that order; in these cases, the sandwich estimator (Diggle and Kenward 1994) will be used to estimate the standard errors of the fixed effects parameters and the denominator degrees of freedom will utilize the DDFM=BETWITHIN option in SAS®.

MIDAS and CSFQ are only collected at baseline and week 12, thus they will be modeled in a ANCOVA similar to the MMRM used for the repeated measures. The model will include fixed effects for treatment, baseline, and stratification factor (preventive medication use). LSMS, standard errors, and the LSM differences (each treatment vs placebo) with 95% CIs and p-values will be reported.

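### Does the early-termination visit rule need a lower day limit before MIDAS and CSFQ-14 scores can count as Week 12?

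*SAP*

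**What the plan says.** SAP 8.1.3 (Assessment Time Windows) assigns ET data "at the closest visit where a given assessment should be collected per the schedule of assessments". It lists Weeks 4, 8, 12 and 14 and says that midpoints between visits set the windows. Baseline is not in the list. The only day limit given is at the late end: "Visits beyond day 112 (two weeks past the target day for Week 14) will not be mapped and reported with Week 14".

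SAP 9.2.2 states that "MIDAS and CSFQ are only collected at baseline and week 12, thus they will be modeled in a ANCOVA". The model terms are treatment, baseline and preventive-medication stratum, with nothing for the day of assessment. SAP 9.2 bases the secondary efficacy analyses on mITT.

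Both scales are completed at the ET visit. Protocol 8.4 includes them among the Visit 5/ET procedures, and Protocol 8.6 says of the ET visit that "assessments and procedures should be completed according to the V5 schedule". Attendance is not certain: patients who withdraw "will be encouraged to complete the ET Visit for safety evaluations (Visit 5) within 7 days from withdrawal of study".

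The scored MIDAS items in Protocol 6.8.3 look back over three months, for example "On how many days in the last 3 months did you miss work or school because of your headaches".

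**The concern.** For MSQ, HADS and PGIC, which are collected at Weeks 4, 8 and 12, an early ET score goes to an early visit. MIDAS and CSFQ-14 have no early slot, so the same patient's scores on these two scales go to Week 12 whenever the patient left. For MIDAS the long recall makes this look worse: a score taken a few weeks into treatment mostly describes the time before it and largely repeats the baseline score. Entered as a Week 12 outcome, it could pull the estimated difference toward zero.

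The wording also leaves some room. One programmer could apply the rule literally, with no floor. Another could take the midpoint clause to mean a Day 43 or a Day 71 cut. The Week 12 data sets would then differ, and a choice made after unblinding could be questioned.

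**Working it through.** The documents give no MIDAS window figure to reproduce, so the check is to apply the rule and size the result.

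**1. Where an ET score goes.** Target days in the schedule are 1 (baseline), 29, 57, 85 and 99.
- Literal reading (listed visits at which the scale is scheduled): Week 12 is the only candidate, so every ET day from Day 2 up to Day 112 maps to it.
- Baseline added as an anchor: midpoint (1 + 85)/2 = 43, so Week 12 takes ET scores after Day 43.
- Midpoints between all listed visits, whatever the scale: (57 + 85)/2 = 71 and (85 + 99)/2 = 92, so Week 12 takes roughly Days 71 to 92.

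**2. Earliest day in mITT.** SAP 4.2 requires 14 diary entries in one 28-day period. Protocol 6.8.5.1 has each day recorded the next morning. The entry for Day 14 is therefore made on Day 15, and Day 15 is the practical floor.

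**3. Pre-treatment share of MIDAS recall.** Take three months as 90 days (assumption). For a visit on Day d the share is (90 − (d − 1))/90.
- Day 15: 76/90 = 84%
- Day 29: 62/90 = 69%
- Day 43: 48/90 = 53%
- Day 71: 20/90 = 22%
- Day 81, the earliest on-window Week 12 visit: 10/90 = 11%
- Average over Days 15 to 70: 48.5/90 = 54% (51% with an 84-day recall, 54% with 91 days)

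**4. Dilution.** The study schema in Protocol 3.1 shows 300 randomized and an estimated 265 completing, so 35 leave early. The documents do not say when. Assume even departure over 84 days and an effect proportional to (d − 1)/84.
- Early ET scores (Days 15 to 70): 35 × 56/84 = 23.3, mean relative effect 41.5/84 = 0.494
- Late ET scores (Days 71 to 84): 35 × 14/84 = 5.8, mean relative effect 76.5/84 = 0.911
- All attend ET: n = 265 + 23.3 + 5.8 = 294.2; pooled effect (265 + 23.3 × 0.494 + 5.8 × 0.911)/294.2 = 0.958, a dilution of 4.2%
- Half attend: n = 279.6, pooled effect 0.978, a dilution of 2.2%

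**5. What a Day 71 cut would achieve.** Compare relative effect × √n, assuming the same spread in early and late scores.
- All attend, early scores kept: 0.9581 × √294.2 = 16.433
- All attend, early scores dropped: n = 270.8, effect 0.9981, index 0.9981 × √270.8 = 16.425
- Interval width, dropped relative to kept: √(294.2/270.8) = 1.042
- Half attend: 16.35 kept and 16.35 dropped; width ratio √(279.6/267.9) = 1.022

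The smaller effect and the larger sample cancel almost exactly.

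**The case for a change.** The strongest argument for changing the text is that a Week 12 label should mean Week 12. MIDAS and CSFQ-14 have no estimand in SAP section 5 that would justify counting an early score as a Week 12 outcome. Elsewhere the SAP leaves late data missing: Month 3 diary counts stay missing below 14 days, and an MSQ or HADS score from Day 29 is used at Week 4. One sentence would remove the ambiguity, and a repeat ANCOVA would show whether it matters.

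The inconsistency between scales is real, and so is the room in the midpoint clause. The case for a specific cut is weaker. Day 71 is a midpoint with Week 8, when neither scale is collected; Day 43, between the two visits at which they are collected, is at least as natural. A Day 71 score is still 22% pre-treatment, and an on-window Week 12 visit on Day 81 is 11%, so mixed recall comes partly from the instrument. The cut would also be keyed to the visit date, although the ET visit may follow withdrawal by a week or so and dosing may already have lapsed. Above all, the ANCOVA has no imputation, so setting early scores to missing removes those patients from the comparison. If they differ from completers, that brings a selection bias which the dilution figures do not count.

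**Conclusion.** No change to the plan follows. Read as written, SAP 8.1.3 gives a single result for a scale with one post-baseline visit, and it keeps in the analysis patients who left early but attended ET. The alternative is a trade-off with no demonstrated gain: sensitivity is the same, intervals are 2% to 4% wider, and the model then sees only those who stayed. What remains is missing detail about the midpoint clause, which analysts would ordinarily settle in the programming specifications before unblinding.

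The stakes are small. At most about 23 of 294 MIDAS scores are affected, fewer if ET attendance is partial. The 2.2% to 4.2% dilution is illustrative: it rests on 35 non-completers, even departure, an effect proportional to treated time and a 90-day recall. The documents give neither the timing of dropout nor its split by arm, so even the direction of any bias is not established.

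CSFQ-14 has the same schedule and the same ANCOVA, so the missing floor applies to it too, but the three-month recall argument is specific to MIDAS. Neither scale belongs to the primary and key secondary set for which SAP 8.1.5 controls type I error, and those endpoints are unaffected.
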